14.4. Proposed Interval Safety Monitoring

The DCC will generate periodic DSMB reports. (We assume the total number of subjects enrolled per six months in a single treatment group will be approximately 30; thus, eight semi-annual looks at the data will be suggested to the DSMB. As usual, though, periods for reporting will be discussed and finalized at the initial DSMB meeting.) Each report will provide cumulative summary statistics on enrollment; subject status in the study (e.g., number completed at 3-month, 6-month, 9-month, and 12month assessments); baseline characteristics; protocol violations; safety data, including AEs and SAEs by AE code, severity, and relatedness to the study medication; outcomes data (if coinciding with an interim analysis—also to be discussed and finalized at the initial DSMB meeting); and data management/quality information (e.g., timeliness and completeness of data entry by the clinical sites via the MISTIE III electronic data capture (EDC) system; number of gueries generated and resolved). Two reports will be generated: an open report with combined data from both treatment groups, and a closed report for the DSMB voting committee members with data provided by blinded treatment group (noted as A and B). The outline of these proposed DSMB reports will be included in the Manual of Operations and Procedures prepared by the CCC. In an interval as yet to be determined (monthly, guarterly, or semi-annually), the CCC will also generate a Safety Monitoring Report to be distributed to the DSMB. This report contains only enrollment, subject study status, safety, and data quality information. The trial's Executive Committee will also receive the Safety Monitoring Reports. The DSMB will have discretion to recommend stopping the trial early if safety concerns become substantial. Safety stopping rules for each of the primary safety outcomes will be developed and used to help the DSMB make its safety assessments.

Minimally Invasive Surgery Plus rt-PA for ICH Evacuation Phase 3

15.0. Tertiary (Exploratory/Sensitivity) Analyses

15.1. Functional Status at 180 and 365 Days Post Ictus

Clot removal with MIS+rt-PA treatment produces improvements in functional outcome will be assessed by alternative outcome measures such as:

- 15.1.a. Glasgow Outcome Scale
- 15.1.b. Barthel Index
- 15.1.c. NIHSS
- 15.1.d. MMSE

Analysis methods will include linear, logistic, and polytomous data models similar to those presented above.

15.2. Quality of Life at 180 and 365 Days Post Ictus

Clot removal with MIS+rt-PA leads to improved health-related QoL and will be assessed by subject and surrogate QoL domains through the:

15.2.a. Stroke Impact Scale

- 15.2.b. PBSI
- 15.2.c. Personal Health Utility Assessment Interview
- 15.2.d. CES-D
- 15.2.e. EQ dimensions individually assessed
- 15.2.f. Home days

15.2.g. Patient location including proportion of days in acute care, home, rehabilitation, long-term care facilities, and in vegetative condition.

Analyses methods will include linear, logistic, and polytomous data models similar to those presented above.

15.3 Cost-Benefit Model

Cost-benefit analyses will be performed using data on median hospital stay, patient disposition categories (such as home, long-term ambulatory and nursing care, death), time to return home, and cost of procedures and hospital stay. These analyses will be performed with respect to both 180- and 365-day periods post-stroke. For cost-benefit analyses, the cost of ICU and the rest of the hospital stay, including the cost of MIS+rt-PA, will be considered. Cost data will be obtained from the literature. The overall amount for both treatments will be assessed, and the difference in dollars will be calculated.

Minimally Invasive Surgery Plus rt-PA for ICH Evacuation Phase 3

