#### **Efficacy Measures Summary.**

- **Primary measure:**

Dichotomized adjudicated mRS 0-3 vs. 4-6 at 180 days post-stroke

- **Secondary measures:**

1. Dichotomized adjudicated mRS at 365 days post-stroke 0-3 vs. 4-6 and 0-2 vs. 3-6
2. Ordinal adjudicated mRS (0 – 6) at 180 days post-stroke
3. Mortality and Safety Events at 30 days post-randomization, including procedure-related mortality, symptomatic bleeding rate, and infection rate
4. Mortality at 180 days post stroke
5. Functional Status: NIHSS, Barthel Index, GOS, extended GOS, MMSE at 180 days post-stroke
6. Type and intensity of ICU management: ICU days, hospital days, patient disposition at 180 and 365 days post-stroke

7. Quality of life: SIS, EQ-5D, PBSI, Personal Health Utility Assessment Interview, days to return to home; patient disposition at 180 and 365 days post-stroke including proportion of days in long-term care facilities
8. Cost: amount of billed and reimbursed

In addition to the primary and secondary measures, there are a number of related and intermediate surrogate outcomes of interest, including Glasgow Coma Score (GCS), Graeb Scale, clot lysis rate and final clot size reduction.

**Safety Measures.** Interim safety analyses will be prepared for the external Data Safety and Monitoring Board (DSMB) on a pre-arranged schedule (such as semi-annual or after enrollment of a fixed number of subjects) to evaluate efficacy and safety. Safety measures include: monitoring the incidence of symptomatic and asymptomatic intracranial bleeding events (i.e., hemorrhage extension, new hemorrhage, catheter-tract hemorrhage) through daily computerized tomography (CT) scans for the first four days after randomization and then repeated one day (approximately 24 hours) after ICH catheter removal, and monitoring the incidence of confirmed and suspected infection and in-hospital mortality.

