Cost-effectiveness Analysis. Cost-benefit and incremental cost-effectiveness analyses will be performed using data on length of hospital stay, patient disposition (home, long-term ambulatory and nursing care, death), time to return home, and cost of procedures and hospital stay. These analyses will be performed with respect to both 180 and 365-day periods post-stroke. For cost-benefit analyses, the cost of ICU and the rest of the hospital stay, including the cost of MIS+rt-PA will be considered. Cost data will be obtained from the trial (secondary outcomes) and from the literature. For the incremental cost-effectiveness analysis, the distribution of hazard rates of changes in mRS and in-hospital stay will be applied between the treatment arms, considering both short-term (acute care) and long-term care post-stroke. The model will include a one-year time horizon and a secondary analysis of life-time horizon. The analysis will be generated from the health care system perspective for costs combined with the quality-of-life measures for effectiveness (i.e. SIS, EQ-5D, and Personal Health Utility Interview). Various measures of effectiveness will be employed and the robustness of the findings to changes in the source of patient utility/quality of life measures will be reviewed. This will be supplemented by looking at ranges for patient utilities reported in the literature. Finally, probabilistic sensitivity analyses will be conducted using a bootstrap approach, producing a scatter plot of incremental costs and effects to assess the impact of statistical uncertainty on the robustness of the conclusions.

**9.1.8. Safety Analyses.** The primary safety measures for this study are symptomatic intracranial bleeding, infection, and 30-day mortality. The safety thresholds for these measures have been set as: 30-day mortality > 60%, first week operative death rate > 10%, a MIS and rt-PA related symptomatic brain bleeding rate > 25% (events identified within the first 30 days and assessed as occurring during active treatment or during the 72 hours after treatment will be monitored), and a procedure-related brain infection rate > 15% (over the initial 30 days).

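### The SAP's tertiary cost-benefit model takes median hospital stay as its stay input, but an overall cost needs the mean, and no interval is attached to the dollar difference

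*SAP*

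**What the plan says.** SAP 15.3 sits among the tertiary (exploratory/sensitivity) analyses. Its opening sentence names the inputs: "Cost-benefit analyses will be performed using data on median hospital stay", followed by disposition categories, time to return home and the cost of procedures and hospital stay. The components are listed next: "For cost-benefit analyses, the cost of ICU and the rest of the hospital stay, including the cost of MIS+rt-PA, will be considered". On the source of costs it says "Cost data will be obtained from the literature". The output is "The overall amount for both treatments will be assessed, and the difference in dollars will be calculated". It gives no formula linking stay to dollars, no confidence interval and no sensitivity analysis for cost.

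Protocol 9.1.7, under Cost-effectiveness Analysis, is different in three respects. The stay input has no median attached: "Cost-benefit and incremental cost-effectiveness analyses will be performed using data on length of hospital stay, patient disposition". The cost source is wider: "Cost data will be obtained from the trial (secondary outcomes) and from the literature". The description ends with a bootstrap of incremental costs and effects. The Efficacy Measures Summary in Protocol 9.1 also lists a cost outcome: "Cost: amount of billed and reimbursed". The outcome list in SAP 2.2 keeps a cost-benefit model but no longer lists billed or reimbursed amounts.

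**The concern.** A total is the number of patients times the mean. If the dollar amount for an arm is obtained by costing its median stay, it describes a middle patient and not the resources the arm used. Patients with very long stays count in a total in proportion to their days, but they barely move a median. Medians also do not add: a median ICU stay plus a median remaining stay is not, in general, the median of the whole stay.

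What is at stake is the reported dollar difference. A reader would take it as the saving or extra expense per patient from adopting the procedure, and a median-based figure does not estimate that. With no interval, the reader also could not see how uncertain it is.

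**Working it through.** **Is there a figure to reproduce?** No. Neither document states a cost, a distribution of stay or a sample size for costs. The only figure on level is in Protocol 2.1, which says ICU stay after a moderately sized haemorrhage averages about a month. Every stay value and spread below is therefore an assumption, used to show the range.

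**Step 1: size of the understatement within an arm.** For a log-normal stay with log-SD *s*, mean = median × exp(*s*²/2). Costing the median understates the expected stay cost by 1 − exp(−*s*²/2).

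| Log-SD | Mean/median | Understatement |
|---|---|---|
| 0.5 | exp(0.125) = 1.133 | 12% |
| 0.7 | exp(0.245) = 1.278 | 22% |
| 0.9 | exp(0.405) = 1.499 | 33% |
| 1.1 | exp(0.605) = 1.831 | 45% |

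**Step 2: effect on the difference, equal spread.** Assume medians of 20 days (MIS+rt-PA) and 22 days (medical), so the median difference is −2.0 days. With log-SD 0.7 in both arms, the mean difference is (20 − 22) × 1.278 = −2.6 days. The sign is kept and the size is understated.

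**Step 3: effect on the difference, unequal spread.** With the same medians:
- log-SD 0.9 v 0.7: 20 × 1.499 − 22 × 1.278 = +1.9 days
- log-SD 0.9 v 0.5: 20 × 1.499 − 22 × 1.133 = +5.1 days

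Over a grid of 0.5 to 0.9 in the medical arm and 0.5 to 1.1 in the MIS arm, the mean difference runs from −10.3 to +11.7 days, while the median difference is −2.0 throughout.

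The sign reverses when *s*²(MIS) − *s*²(medical) > 2 ln(median medical / median MIS). With medical log-SD 0.7 and a median ratio of 0.90, the MIS log-SD must exceed √(0.49 + 2 ln(1/0.90)) = √0.701 = 0.84. With a ratio of 0.95 it must exceed √(0.49 + 0.103) = 0.77.

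**Step 4: a fixed procedure cost, equal spread.** The SAP adds the cost of MIS+rt-PA to one arm. Suppose the median saving is 3 days. At log-SD 0.7 the mean saving is 3 × 1.278 = 3.8 days. If the procedure costs the equivalent of between 3.0 and 3.8 hospital days, the median-based model reports a net loss where the mean-based model reports a net saving. At log-SD 0.5 the band is 3.0 to 3.4, and at 0.9 it is 3.0 to 4.5. Outside the band the net sign agrees.

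**Step 5: could the arms differ in shape?** Phase II 30-day mortality was 10% medical and 15% surgical (Protocol 2.2, Mortality), so the mix of short and long stays could differ. A simulation used those rates, with assumed median stays of 6 days for early deaths (log-SD 0.7) and 25 days for survivors in both arms:

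| Survivor log-SD, MIS v medical | Median difference | Mean difference |
|---|---|---|
| 0.7 v 0.7 | −1.2 days | −1.2 days |
| 0.8 v 0.7 | −1.6 days | +0.9 days |
| 0.9 v 0.7 | −2.1 days | +3.5 days |

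Unequal mortality alone did not reverse the sign. An additional difference in survivor spread was needed.

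**The case against.** Five points can be made for the plan.

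- **Median stay is one input among several.** Disposition, time to return home, and procedure and stay costs are listed beside it, and there is no formula. Multiplying a daily cost by the median stay is the natural reading, but it is an inference. This stands: it would be too strong to say the whole dollar difference is a function of the median.
- **A reader might infer that the model will favour the wrong arm.** The documents do not support that. They give no spread for either arm, and with equal spread the stay component keeps its sign. Protocol 2.2 reports the same ICU stay in both phase II arms and 37 days more care before return home for medical subjects. The latter enters SAP 15.3 through separate inputs. Reversal is a possibility whose probability cannot be computed.
- **Means will be available.** SAP 1.0 includes the mean among the summaries of continuous variables, and SAP 13.6 models hospital and ICU days. This lowers the cost of the change. It does not alter which summary SAP 15.3 feeds into the cost, and nothing else in the SAP restores a mean for that purpose.
- **Literature costs may be a reasonable choice.** Billed and reimbursed amounts appear only as a listed measure, with a general reference to trial cost data in Protocol 9.1.7. No cost item appears in the schedule of evaluations (Protocol 6.1) or among the source uploads in Protocol 10.3.9. A reader might infer that the SAP discards billing data in hand, but the documents do not show that such data were collected. This stands.
- **The bootstrap belongs mainly to the protocol's incremental cost-effectiveness analysis**, which SAP 15.3 does not describe. That is fair as to its origin, but a dollar difference still needs a measure of uncertainty, and SAP 15.3 supplies none.

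**Conclusion.** The point holds in a limited form. The stay input named in SAP 15.3 is a median, its output is an overall amount and a difference, and a median does not estimate the mean that such an amount requires. The size depends on an assumption of right skew that the documents neither state nor contradict. Under a log-normal shape the stay component is understated by about 12% to 45% for log-SD 0.5 to 1.1. The between-arm difference is distorted by an amount that cannot be fixed from the documents. A changed sign needs unequal spread between arms or a procedure cost inside a limited band.

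The model is tertiary, with no hypothesis test or decision rule attached, so the trial's primary, secondary and safety conclusions are unaffected. The correction is minor in priority but specific.

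**What to change.** In SAP 15.3, replace the median stay input with patient-level hospital and ICU stay, summarized by the arithmetic mean. Report mean cost per randomized patient by arm and the difference in means, with a bootstrap 95% confidence interval obtained by resampling patients within arm. Keep medians as descriptive statistics. State the formula that turns stay, disposition and procedure use into dollars. Use trial billed or reimbursed amounts where they were collected and literature unit costs otherwise, and say which source was used for each component.

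Stay needs no new data, because hospital and ICU days are already analysed under SAP 13.6. The cost is a short wording change and a little more analysis time. The downside is an interval that may be wide.
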